1.1.6 Dose Rationale and Risks/Benefits

1.1.6.1 Dose Rationale for Venetoclax

The dose limiting toxicity in venetoclax is primarily hematologic (cytopenias). In the CAVELLI phase Ib trial of an escalating dose of venetoclax in combination with either obinutuzumab-CHOP or rituximab-CHOP, the hematologic toxicity of venetoclax was found to be dose and time-dependent, and reductions in dosing frequency were required in combination with chemotherapy. A recommended phase 2 dose of 800 mg days 4 to 10 of cycle 1 and days 1 to 10 of cycles 2 to 8 was

established (Zelenetz et al. 2019). As monotherapy, the maximum tolerated dose was not reached in a phase I trial of venetoclax in NHL (Davids et al. 2017). However, 9 of the 51 patients treated at 1200 mg required dose reduction due to GI side effects in that trial. The combination of venetoclax and rituximab or obinutuzumab has also been studied in CONTRALTO (Zinzani et al. 2018) and SAKK 35/15 (Stathis et al. 2019) trials, both with an established recommended dose of venetoclax of 800 mg daily continuously. The optimal dose of venetoclax in combination with other targeted agents such as azacitidine is not established in FL and will be investigated in the phase I portion of this trial. The highest dose level in this trial will be 800 mg daily, due to the potentiating effect of combination therapy on both efficacy and toxicity.

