1.2.2 Objectives for Dose Finding Cohort

1.2.2.1 Co-Primary Objective of the Dose Finding Cohort

Determine the RP2D of combined venetoclax/CC-486 in patients with minimally pre-treated FL.

Hypothesis: Dose limiting toxicities will not be uncovered at the maximum recommended doses discussed with the manufacturer; an RP2D will be established at 800 mg venetoclax and 200 mg CC-486.

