2.7 PRIMARY STUDY ENDPOINTS

Dose-finding cohort:

- Recommended phase 2 dose, defined as the maximum tolerated dose up to dose level 3 (see Table 2)
- Rate of grade 3/4 adverse events
- Rate of discontinuation

Expansion cohort:

• Six-month complete metabolic response rate assessed by PET scan

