4.2 DRUG REGIMEN

4.2.1 Summary of Drug Regimen

4.2.1.1 Summary of Drug Regimen for Dose Finding Cohort

In the dose-finding cohort, there will be three escalating dose levels of the three drug combination, and two optional dose de-escalation levels if needed (see Table 2). Venetoclax will be dosed by mouth once daily on days 1-28 or days 1-10 of each 28-day cycle. CC-486 will be dosed by mouth once daily on days 1-14. The doses and days of administration of CC-486 and venetoclax for each dose level are found in Table 2. Obinutuzumab will be administered intravenously at a fixed dose of 1000 mg on days 1, 8, and 15 of cycle 1, and on day 1 of each subsequent cycle. 12 total cycles will

be completed of venetoclax and CC-486. Obinutuzumab will be administered for 9 total cycles (cycle 1-9) and omitted from cycle 10-12. Definition of DLT is in Section 6.2.1.

Table 2: Levels for dose finding

Dose Level	Venetoclax	CC-486	Obinutuzumab
DL 1	400 mg days 1-28	200 mg days 1-14	1000 mg
DL 2	600 mg days 1-28	200mg days 1-14	1000 mg
DL 3	800 mg days 1-28	200 mg days 1-14	1000 mg
DL -1	400 mg days 1-28	150 mg days 1-14	1000 mg
DL -2	400 mg days 1-10	150 mg days 1-14	1000 mg

[figure not shown]

Figure 3: Treatment plan for dose-finding arm

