6 STATISTICAL PLAN AND CONSIDERATIONS

6.1 SAMPLE SIZE DETERMINATION

The sample size of the dose-finding arm may vary based on the number of adverse events in the lower dose levels, with an estimated size of 12-18 subjects. The number of subjects for the expansion cohort was calculated using $\alpha = 0.1$, $\beta = 0.2$, power $(1 - \beta) = 0.8$, a dichotomous study outcome, null hypothesis (H0) proportion of 0.3, and an alternative hypothesis proportion of 0.5. Enrolling 32 patients in a Simon two-stage design yields an α of 0.0997, 1- $\beta = 0.8038$, and a probability of correctly stopping after 15 patients if the null hypothesis is true of 72.16%.

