6.2 STATISTICAL METHODS

6.2.1 Dose Finding Cohort

A 3+3 trial design with 3 dose levels and 2 optional dose de-escalation levels will be used (see Section 4.2 for details). This rule-based design proceeds with cohorts of three patients; the first cohort is treated at a starting dose that is considered to be safe based on prior human studies, and the subsequent cohorts are treated at increasing dose levels that have been fixed in advance (Storer 1989). Safety and tolerability for the purpose of dose-finding for the three-drug combination will be assessed in the first 28-day cycle of therapy.

The definition of dose limiting toxicity (DLT) is as follows:

- Grade 3 or 4 treatment-related non-hematologic toxicity with the exceptions of fatigue, anorexia, nausea, and fever without neutropenia
- Grade 4 treatment-related hematologic toxicity (anemia, thrombocytopenia and/or neutropenia) either lasting > 7 days despite supportive care or complicated by hemorrhage
- Any grade 5 toxicity.

If none of the three patients in the first cohort experiences a DLT within a 28-day cycle, the dose level will be advanced to DL2. If one or more of the patients at a certain dose level experiences a dose-limiting toxicity, three more patients will be treated at the same dose level. If there are two or more DLTs in a cohort of 3-6 patients at dose level 1, three patients will be enrolled at DL-1. If there are two more DLTs at dose level -1, three patients will be enrolled at DL-2.

If the dose level has been advanced to level 2 already, and two or more patients in a cohort of 3-6 patients experience dose-limiting toxicity, the RP2D will be defined as dose level 1. If a dose level has been lowered to DL-1 or DL-2 and no patients experience a DLT, that dose will be the RP2D. If one patient in a cohort at DL-1 and DL-2 experiences a DLT, another three patients will be enrolled. If none of the subsequent cohort experience a DLT, the dose level will be taken as the RP2D.

If there are no DLTs at DL2, DL2 will be the RP2D.

NOTE: The RP2D will be determined based on an integrated evaluation of the efficacy, safety, and tolerability of all evaluated dosing cohorts.

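### Section 6.2.1 ends escalation at DL2, so DL3, the plan's top level and hypothesised RP2D, can never be opened; 1/6 DLTs at DL1 or DL2 also has no stated action

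*Combined protocol and SAP*

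**What the plan says.** Section 6.2.1 announces a 3+3 with three dose levels and two optional lower ones. Its specific rules are:

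- **DL1, 0/3 DLTs:** go to DL2.
- **Any level:** "If one or more of the patients at a certain dose level experiences a dose-limiting toxicity, three more patients will be treated" at that level.
- **DL1, at least two DLTs among three to six patients:** go to DL-1. From DL-1, a further two or more lead to DL-2.
- **DL2, at least two DLTs among three to six patients:** the RP2D is DL1.
- **DL2, no DLTs:** "If there are no DLTs at DL2, DL2 will be the RP2D".
- **DL-1 or DL-2:** 0/3 makes that level the RP2D. One DLT adds three patients, and the level is accepted if those three have none.

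A closing note makes the final RP2D an overall judgement across the cohorts that were evaluated.

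Other sections place the ceiling one level higher:

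- Section 4.2.1.1: "there will be three escalating dose levels of the three drug combination". Table 2 there lists DL1, DL2 and DL3 as venetoclax 400, 600 and 800 mg, each with CC-486 200 mg.
- Section 1.1.6.1: "The highest dose level in this trial will be 800 mg daily".
- Section 2.7, primary endpoint: "Recommended phase 2 dose, defined as the maximum tolerated dose up to dose level 3".
- Section 1.2.2.1, hypothesis: "Dose limiting toxicities will not be uncovered at the maximum recommended doses", and "an RP2D will be established at 800 mg venetoclax and 200 mg CC-486".
- Section 6.1, size of the dose-finding arm: "with an estimated size of 12-18 subjects".

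**The concern.** The section that runs the escalation contradicts the sections that define its goal. It never names DL3. A clean result at DL2, which in a 3+3 is the reason to go up, is instead the reason to stop.

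The RP2D is a primary endpoint and fixes the expansion regimen (Section 4.2.1.2). Under Section 6.2.2, patients treated at that dose in the dose-finding arm also count toward expansion accrual, so uncertainty about the RP2D carries into the Simon test. If investigators infer that DL3 should be opened, they give the highest dose of a new triplet with no written stopping rule for it, and they depart from an explicit sentence to do so.

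Two smaller gaps sit in the same rules. One DLT in six patients, a routine 3+3 outcome, has a stated action only at DL-1 and DL-2. And the expansion rule is triggered by one or more DLTs, so it overlaps the rules for two or more.

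**Working it through.** **Following the rules upward**

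| Level | 0/3 | 1/6 (1/3, then 0/3) | Two or more DLTs |
|---|---|---|---|
| DL1 | go to DL2 | not stated | go to DL-1 |
| DL2 | RP2D = DL2 | not stated | RP2D = DL1 |
| DL3 | not stated | not stated | not stated |

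No cell leads to DL3.

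**Sample size.** Section 6.1 gives 12-18 with no formula, so it can only be compared with candidate rules.

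- Rules as written, upward path: 3 + 3 = 6, or 3 + 6 = 9. DL1 contributes only three patients because DL2 opens only after 0/3.
- DL3 open, 0/3 accepted there: 3 + 3 + 3 = 9 to 6 + 6 + 6 = 18.
- DL3 open, six patients at the MTD: 3 + 3 + 6 = 12 to 6 + 6 + 6 = 18.

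Only the last matches 12-18 exactly. Under the written rules, 18 patients are reached only by de-escalating through DL-1 and DL-2.

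**Probabilities.** The documents give no DLT rates. Assume the same rate p at DL1 and DL2 and use exact binomial probabilities.

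- (a) Written rule stops at DL2 with no DLTs: (1-p)^3 × (1-p)^3 = (1-p)^6.
- (b) 1/6 at a level that is entered: 3p(1-p)^2 × (1-p)^3 = 3p(1-p)^5.
- (c) Written rules run into an unaddressed 1/6 at DL1 or DL2: (b) + (1-p)^3 × (b).
- (d) Conventional 3+3 passes a level: (1-p)^3 + 3p(1-p)^5. It opens DL3 with probability (d)^2.
- (e) At least two DLTs in the first three, where the expansion rule overlaps the stopping rules: 3p^2(1-p) + p^3.

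| p | (a) | (b) | (c) | (d) | (d)^2 | (e) |
|---|---|---|---|---|---|---|
| 5% | 0.735 | 0.116 | 0.216 | 0.973 | 0.948 | 0.007 |
| 10% | 0.531 | 0.177 | 0.306 | 0.906 | 0.821 | 0.028 |
| 20% | 0.262 | 0.197 | 0.297 | 0.709 | 0.502 | 0.104 |
| 30% | 0.118 | 0.151 | 0.203 | 0.494 | 0.244 | 0.216 |

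Worked line, p = 10%: (a) 0.9^6 = 0.531; (b) 0.3 × 0.9^5 = 0.177; (c) 0.177 + 0.729 × 0.177 = 0.306; (d) 0.729 + 0.177 = 0.906, squared 0.821; (e) 0.027 + 0.001 = 0.028.

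At p = 0, the plan's own hypothesis, (a) is 1: the trial stops at 600/200 mg after six patients. The probability that the written rules open DL3 is 0 at every p.

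**The case against.** The best defence is that the intent is plain. Sections 1.1.7 and 2.1 call the design a standard 3+3, and Section 6.2.1 itself speaks in general terms of later cohorts moving up through prespecified doses. A reader who knows the method would open DL3 and treat 1/6 as permission to escalate. The DL2 sentence may be a slip for DL3. Stopping at 600 mg is also the cautious error, and the closing note leaves the final RP2D to judgement.

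Part of this stands. The 1/6 gap can be filled from convention, and no written sentence contradicts that reading, so it is secondary. The expansion wording is a drafting repair, since the neighbouring rules show that exactly one DLT was meant. The 12-18 figure is an estimate that the plan says may vary, so it supports the reading that DL3 was intended but proves nothing. The probabilities rest on assumed rates, and the contradiction does not need them. Figure 3 in Section 4.2.1.1 is missing from the text reviewed; its caption suggests a treatment schedule, and no figure would remove the DL2 sentence.

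The main point survives. A general label gives no DL2-to-DL3 criterion and cannot override an explicit contrary rule. The note covers only evaluated cohorts, and DL3 would never be one. Reading DL3 for DL2 in the faulty sentence still leaves no step from DL2 to DL3 and no action for two or more DLTs at DL3.

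**Conclusion.** The concern holds and should be fixed. Section 6.2.1 is wrong as written, not merely brief: followed literally, it cannot reach the dose that Sections 1.1.6.1, 1.2.2.1, 2.7 and 4.2.1.1 treat as the top of the range. This conclusion rests on the text alone.

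Its practical size depends on the true DLT rate. At assumed equal rates of 5% to 30% at DL1 and DL2, a conventional 3+3 would open DL3 with probability 95% falling to 24%, against zero under the written rules. The conflict is sharpest where the plan expects to be: with no DLTs, the literal rule is certain to name 600/200 mg. The unaddressed 1/6 outcome is met in about 20% to 31% of trials over the same four rates, but it is a clarification beside the DL3 contradiction.

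**What to change.** Rewrite the rules in Section 6.2.1:

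1. Expand a level from three to six patients when exactly one of the first three has a DLT.
2. At DL1 or DL2, 0/3 or 1/6 escalates to the next level.
3. Two or more DLTs in three to six patients stop enrolment at any level. DL1 then goes to DL-1, DL-1 to DL-2, and DL-2 ends dose finding. At DL2 the RP2D is DL1; at DL3 it is DL2.
4. Replace the DL2 sentence: if 0/3, or no more than 1/6, have a DLT at DL3, then DL3 is the RP2D.
5. Align Section 6.1 with the choice made at DL3. Accepting 0/3 there gives 9-18 patients on the upward path. Requiring six at the MTD gives 12-18 and matches the present estimate; in that case, item 4 should require no more than 1/6.

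If the sponsor does mean DL2 to be the ceiling, keep the DL2 sentence and correct the Study Summary (dose range and number of levels), Sections 1.1.6.1, 1.2.2.1, 2.1, 2.7 and 4.2.1.1 with Table 2, and the opening of Section 6.2.1. A rule for 1/6 at DL1 and DL2 is needed either way.

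The cost is protocol wording, with no new procedures. The path through DL3 stays within the stated maximum of 18 patients.

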6.2.2 Expansion Cohort

Prior to start of the expansion cohort, there will be a review of the dose modification plan for the expansion cohort by the PI and co-I's. Based on prior studies of chemotherapy-sparing front-line agents in FL (Morschhauser et al. 2018), we hypothesize a successful combination will demonstrate a complete response rate of greater than 50%, while an ineffective combination will demonstrate a complete response rate of less than 30%. Simon's two-stage design (Simon 1989) will be used to test the primary outcome of 6-month CR rate defined for each subject as a binary categorical variable using Lugano response criteria applied to the 6 month PET disease assessment. The null hypothesis that the true 6-month CR rate is 30% or lower will be tested against a one-sided alternative. In the first stage, 15 patients will be accrued. If there are 5 or fewer responses in these 15 patients, the study will be stopped. Otherwise, 17 additional patients will be accrued for a total of 32. The null hypothesis will be rejected if 13 or more responses are observed in 32 patients. This design yields a type I error rate of 0.10 and power of 0.80 when the true response rate is 50%. Patients treated at the MTD/RP2D in the Dose Finding Cohort will contribute towards the accrual goal for the Expansion Cohort.

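### Section 6.2.1 stops escalation at DL2 (600 mg) and has no rule for DL3, although the RP2D endpoint, the dose table and the hypothesis all run to DL3 (800 mg)

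*Combined protocol and SAP*

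**What the plan says.** **Rules in 6.2.1 (Dose Finding Cohort).** The section announces a 3+3 design with three dose levels and two optional de-escalation levels. The rules it then writes out are these:
- No DLT in the first three patients at DL1 advances to DL2.
- One or more DLTs at a level adds three patients at that level.
- Two or more DLTs in 3 to 6 patients at DL1 leads to DL-1. At DL2, the same result makes DL1 the RP2D.
- At DL-1 and DL-2, no DLT makes that level the RP2D. One DLT adds three patients, and if none of those has a DLT the level is the RP2D.
- "If there are no DLTs at DL2, DL2 will be the RP2D".
- A closing NOTE: "The RP2D will be determined based on an integrated evaluation of the efficacy, safety, and tolerability of all evaluated dosing cohorts".

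**Elsewhere in the protocol.**
- 2.7, primary endpoint: "Recommended phase 2 dose, defined as the maximum tolerated dose up to dose level 3 (see Table 2").
- 4.2.1.1: "there will be three escalating dose levels of the three drug combination". Table 2 in that section gives DL1, DL2 and DL3 as 400, 600 and 800 mg venetoclax on days 1-28, each with 200 mg CC-486.
- 1.1.6.1: "The highest dose level in this trial will be 800 mg daily".
- 1.2.2.1, hypothesis: "an RP2D will be established at 800 mg venetoclax and 200 mg CC-486".
- 6.1, dose-finding arm: "with an estimated size of 12-18 subjects".

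**The concern.** The RP2D is a primary endpoint, and under 4.2.1.2 it is the dose given to the expansion cohort. The rule that produces it ends one level below the ceiling in its own endpoint definition. The two texts part at the result the sponsor predicts, which is no dose-limiting toxicity. A site or safety call following 6.2.1 would close dose finding at 600 mg, while one following 2.7 and Table 2 would enrol at 800 mg. Choosing between them after the DL2 data are in would be an unplanned decision about a primary endpoint.

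The missing outcome for one DLT in six, and the clash between the two rules after two DLTs in three, leave other ordinary 3+3 results without a clear instruction. The clash bears on safety, because one of the two rules keeps enrolling at a level that has already failed.

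**Working it through.** **1. The plan's own figure.** Section 6.1 gives 12-18 patients without a derivation. With 3 or 6 patients per level:
- stopping at DL2: 3+3, 3+6 or 6+6 = 6, 9 or 12;
- three upward levels: 9, 12, 15 or 18;
- downward path DL1, DL-1, DL-2 with six each: 18.

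The range fits three upward levels better than a stop at DL2. But 12 also fits the two-level path and 18 the downward path, so it does not settle the intent.

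**2. The texts side by side.**

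| Result | Rule in 6.2.1 | 2.7, 4.2.1.1, Table 2, 1.1.6.1 |
|---|---|---|
| 0/3 at DL1 | go to DL2 | go to DL2 |
| 1/6 at DL1 | none stated | no rule |
| 0/3 at DL2 | RP2D is DL2, 600 mg | DL3 must be opened to find the MTD up to DL3 |
| 1/6 at DL2 | none stated | no rule |
| 2/3 or 3/3 at DL1 or DL2 | add three at that level, and also move to DL-1 (from DL1) or declare DL1 (from DL2) | no rule |
| Any result at DL3 | none stated | no rule |

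**3. Reaching 800 mg under 6.2.1.** No written rule opens DL3, so the probability is 0 at every DLT rate. With no true toxicity, DL1 and DL2 are both clean with probability 1, and DL2 is declared the RP2D with probability 1. The 800 mg hypothesis cannot be met by following the rule.

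**4. How often this matters.** The documents give no DLT rates, so p1, p2 and p3 (at DL1, DL2 and DL3) are assumptions.
- 6.2.1 stops at a clean DL2, counting only its written 0/3 trigger at DL1: S = (1−p1)³(1−p2)³.
- A level passes at 0/3 or 1/6: pass(p) = (1−p)³ + 3p(1−p)⁵.
- DL2 is declared although DL3 would have passed: S × pass(p3).
- 1/6 at DL1, or 0/3 at DL1 then 1/6 at DL2: G = 3p1(1−p1)⁵ + (1−p1)³ × 3p2(1−p2)⁵.

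| p1/p2/p3 (%) | S | pass(p3) | S × pass(p3) | G |
|---|---|---|---|---|
| 5/5/5 | 0.735 | 0.973 | 0.72 | 0.216 |
| 10/10/10 | 0.531 | 0.906 | 0.48 | 0.306 |
| 20/20/20 | 0.262 | 0.709 | 0.19 | 0.297 |
| 10/15/20 | 0.448 | 0.709 | 0.32 | 0.323 |
| 10/20/30 | 0.373 | 0.494 | 0.18 | 0.320 |

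For 10/15/20%: S = 0.9³ × 0.85³ = 0.729 × 0.614 = 0.448, and 0.448 × 0.709 = 0.32. The flat-rate rows assume that toxicity does not rise between 400 and 800 mg. The last two rows are the more realistic ones, since 1.1.6.1 reports dose-dependent haematologic toxicity in combination with chemotherapy.

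**5. Two or more DLTs in the first three patients.** At one level with true rate p, the probability is 3p²(1−p) + p³: 0.007 at 5%, 0.028 at 10% and 0.104 at 20%.

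**6. With 0/3 or 1/6 opening the next level.** DL3 is opened with probability pass(p1) × pass(p2) and becomes the RP2D with probability pass(p1) × pass(p2) × pass(p3). At 10/15/20% these are 0.74 and 0.52. At 10/20/30% they are 0.64 and 0.32.

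**The case against.** **Escalation is implied.** 6.2.1 describes cohorts at rising, pre-set levels, so a team could be said to know that DL3 follows DL2. That sentence is a general description of the method. It gives no trigger for DL3 and cannot displace an explicit sentence that makes DL2 the RP2D.

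**The NOTE gives flexibility.** It covers only cohorts already evaluated, so it cannot select a level that was never opened. A reader might infer the opposite danger, that the NOTE lets the team go above the MTD. The documents do not support that: 2.7 defines the RP2D as the MTD up to DL3, which is a ceiling. What is left open is only whether the team may go lower, and that is a missing detail.

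**The same DLT data do not give two doses.** A reader might infer that one set of DLT results yields 600 mg under one section and 800 mg under another. This objection stands. The other sections lead to opening DL3, and 800 mg would then need DLT data from DL3 itself. The contradiction is stop versus continue.

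**The probabilities rest on assumed rates.** This also stands, and they only illustrate scale. The contradiction needs none of them.

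**Conclusion.** The point holds. As written, 6.2.1 fixes the primary-endpoint dose at 600 mg after a clean DL2 cohort and can never reach the 800 mg that the endpoint definition, dose table, dose rationale and hypothesis provide for. That conclusion comes from the text alone. On assumed rising DLT rates, and counting only the written 0/3 trigger at DL1, the trial would stop at 600 mg although DL3 would have passed with probability 0.32 (10/15/20%) or 0.18 (10/20/30%). The unstated 1/6 outcome has probability about 0.22 to 0.32 for rates of 5 to 20% at DL1 and DL2.

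A reader might go further and infer that the type I error of the expansion cohort is inflated, because the NOTE names efficacy and 6.2.2 says "Patients treated at the MTD/RP2D in the Dose Finding Cohort will contribute towards the accrual goal for the Expansion Cohort". The documents do not establish this. They do not say that those patients enter the Simon count, and any inflation would depend on response rates and dose choices that are not given. It is a separate question about the expansion cohort. The Simon figures in 6.1 (α 0.0997, power 0.8038, early stopping 72.16%) reproduce by exact binomial calculation and are untouched by this point.

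This should be fixed: it affects a primary endpoint, and the correction is short.

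**What to change.** In 6.2.1:
1. Replace the DL2 sentence with: *0/3 DLTs, or 1/6 after expansion, at DL1 or DL2 opens the next level. At DL3, 0/3 or 1/6 makes DL3 the RP2D. Two or more DLTs at DL2 or DL3 makes the next lower level the RP2D.*
2. In the expansion rule, change *one or more* to *exactly one*, so that two or more DLTs stops accrual at that level.
3. Add to the NOTE that the integrated evaluation may keep or lower the DLT-based MTD but not exceed it, consistent with 2.7.

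If DL2 is the intended maximum, leave the DL2 sentence and correct 2.7, 1.1.6.1, 1.2.2.1, 4.2.1.1, Table 2 and the count of three levels in 6.2.1. Items 2 and 3 and an outcome for 1/6 at DL1 and DL2 are needed in either case.

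The cost is a few sentences in an amendment. Opening DL3 takes 3 to 6 patients, and three full levels use at most 18, the upper end of the range in 6.1.
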